## 2.2.4 To promote scientific investigation

A large FMT registry will provide an unprecedented and rich resource for investigators to advance the science of the gut microbiome in health and disease. The registry database will be available to investigators, with study proposals submitted for review by a Data Access and Publications Committee. Furthermore, this registry data will link to a biobank of fecal samples from the donor (one time) as well as recipient (before and after FMT). Together with the clinical metadata collected within the registry, information from analysis of specimens in the biobank will enhance short- and long-term safety surveillance as well as be a rich source of data to investigate modulation of the human gut microbiome.

#### 2.2.5 To aid practitioners and sponsors in satisfying regulatory requirements

The FDA is currently determining the appropriate regulatory requirements for physicians performing FMT, exercising enforcement discretion regarding an IND requirements for use of FMT in treatment of CDI unresponsive to standard therapies. Participation in the FMT Registry provides an excellent method of oversight, helping to prevent marked departures in methodology from recommended practices, improve safety for patients, and gather data for quality improvement and future regulatory requirements. In addition, gut-related-microbiota products, from processed stool to defined microbiota consortia, require submission for regulatory approval. The Registry may function as an important vehicle for sponsors of gut-related microbiota products to satisfy preapproval and post-approval assessment of product safety and efficacy.

## 3 STUDY DESIGN

## 3.1 Overview Study Design Summery

This registry will prospectively enroll 4,000 patients who undergo FMT at 75 sites throughout North America. Information on FMT methodology employed (e.g., screening of donor and recipient, preparation, FMT delivery) will be collected from each site. The indication for FMT as well as baseline information on recipient will also be collected. Following FMT, patients will be followed at regular intervals up to 10 years post FMT. This will include follow-up information from the patient's healthcare provider at 1 month, 6 months, 1 year, and 2 years after FMT as well as direct communication with patients at least annually up to 10 years after FMT. Follow-up information collected will be designed to assess potential short-term and long-term safety and effectiveness.

Anticipating changes in therapy from current FMT to use of other gut-related microbiota products in coming years, the Registry will be constructed with the flexibility to collect methodological and follow-up clinical information for all forms of gut-related-microbiota products and for a variety of indications besides CDI and IBD.

#### 3.2 Site Selection

Sites currently performing FMTs will be allowed to participate in the FMT registry. Sites may utilize any method of FMT treatment or may provide other gut-related microbiota products.

Sites selected to participate in the registry must demonstrate that all study staff have completed human subjects protection and HIPAA training prior to enrollment. Study staff must pass training on informed consent procedures, the electronic case report form (eCRF) system for data recording, and reporting procedure for unexpected events. Sites must demonstrate proper data protection procedures prior to participant enrollment. All site Principal Investigators must sign an Investigators Agreement and confirm IRB approval prior to site activity starting.

Sites will be chosen based on the following criteria: 1) FMT volume; 2) geographic location; 3) ability and willingness to comply with the requirements of registry participation; 4) have an IRB-approved protocol. In the initial phase, we will include the centers of the investigators on this proposal (n=5) and 20 centers from our listserv of 70 centers representing thought leaders in FMT with an interest in clinical investigation. To enhance representation of a geographically diverse population in the registry, centers will be related to their location in population-based regions. Using the projected number of FMTs at each center, we will enroll the number of centers in each region required to achieve a proportion of FMTs in the registry from a region to approximately mirror the proportion of the U.S. population in that region.

## 4 STUDY ENROLLMENT

## 4.1 Subject Inclusion Criteria

Participants will be eligible for participation regardless of age, race, ethnicity, or gender. Pediatric patients may participate if consent is given by a guardian.

#### 4.1.1 Recipient Inclusion Criteria

- Ability to give informed consent
- Receiving FMT or other gut-related microbiota product within 90 days after providing consent
- Access to internet and/or [contact] Donor Inclusion

- Ability to give informed consent
- Providing stool sample for FMT

## 4.2 Subject Exclusion Criteria

Incarceration

## 4.3 Strategies for Recruitment and Retention

Participants who are being seen in clinical practice as an FMT recipient (or FMT donor) or as a recipient of other gut-related-microbiota products will be approached in a private room to receive information about the registry protocol, the option to participate in a biorepository sub-study, review the informed consent documents, and to ask questions and review the risks and benefits of participation. Participants will have as much time as they would like to review the documents and ask questions regarding participation.

## 4.4 Subject Withdrawal

#### 4.4.1 Early Withdrawal of Participants

Participants may end their participation at any time by notifying the study staff of their desire to halt participation. This may be done in writing or by secure internet connection. Registry mailing address and electronic address will be provided to all participants.

#### 4.4.2 Data Collection and Follow-up of Withdrawn Participants

When participants notify study staff that they no longer wish to participate, study staff will request final-visit information from the participant and their healthcare provider. If the participant informs the study staff that they wish to withdraw consent, no further data will be sought from them or their healthcare provider. Data that was previously collected when the patient was actively enrolled will be retained in the registry.

## 4.5 Costs and Payments

This is not a clinical treatment study and all costs associated with the care and treatment of patient receiving FMT and follow-up will be paid by the patient or their insurance provider. No costs will be incurred by participants related to participation in the Registry. Continued patient participation will be encouraged with a \$10 gift card for providing health information each year beginning 1 year post-FMT.

#### 5 STUDY PROCEDURES AND EVALUATIONS

The only study procedure will be data collection regarding methodology of FMT, characteristics and health outcomes of recipients of FMT or other gut-related-microbiota products, and baseline characteristics of donors of stool for FMT.

#### **5.1** Data Elements

Data elements that may be collected for the FMT registry are shown in Supplements 1-6. In order to make the data elements as broad and inclusive as possible, the FMT Registry Steering Committee developed the data elements based on current guidelines and published recommendations, their own treatment protocols/experience, and feedback from 15 additional large FMT practice sites. *Supplement 1* details the data elements related to FMT technique including donor and recipient screening. For sites that employ a donor questionnaire, *Supplement 2* provides potential questions used on a questionnaire, based on those used for blood transfusion. *Supplement 3* shows the data elements for baseline characteristics of donors and recipients and for FMT treatment indications, while *Supplement 4* provides effectiveness outcomes data elements. Finally, *Supplements 5* and 6 detail data elements for short-term and long-term safety outcomes. Patients will be followed at regular intervals for up to 10 years after FMT for pre-defined and spontaneously reported adverse events and for pre-defined outcomes of effectiveness. Investigators will enter follow-up data at 1 month, 6 months, 1 year and 2 years post-FMT, and patients will then provide data annually up to 10 years.

## 5.2 Study Specific Biospecimens and Biorepository Sub-Study

No biospecimens will be collected as part of this registry. However, participants have the option to enroll in a Biorepository Sub-Study and provide stool specimens to be stored in a biorepository that will be linked to their registry data. The biorepository will be maintained by the American Gut Project at University of California at San Diego. Currently, we plan to link data from at least 1,000 FMT procedures for participants in the registry to this biorepository, with 3 stool specimens for each FMT: a donor stool specimen and 2 recipient stool specimens (before and after FMT). The Biorepository Sub-Study protocol is described in *Appendix A*.

## 6 ASSESSMENT OF SAFETY

Details about participant risk and potential benefits are detailed in informed consent. AEs experienced by participants involved in this registry will be reported to the site's IRB in accordance with their procedures.

#### 6.1 Adverse Events

Based on numerous case reports and small clinical studies in the literature, it appears that FMT for refractory CDI is generally well-tolerated and safe, although occasional adverse events (e.g., febrile

episodes) have been reported. Importantly, a prospective systematic evaluation of both immediate and short-term predefined adverse outcomes in a large number of patients undergoing FMT is currently lacking. In the absence of any consensus guideline on practice standards for FMT in the U.S. and the lack of regulatory oversight for the treatment of refractory CDI, the committee has learned through polling of sites performing FMT that there is a wide variation in the practice of FMT. This variance in practice also raises potential concerns about risks for both short-term and long-term risks. As discussed in section 5.1, to broadly capture adverse outcomes in recipients of FMT that may be indicative of a safety concern, we have developed two data entry fields: 1) Short-Term Adverse Outcomes (within 30 days)—Supplement 5, and 2) Long-term Adverse Outcomes (up to 2 years reported by the physician and 10 years reported by the patient)—Supplement 6. Adverse event information will be provided by the FMT provider site at four time points post-FMT: 1 month, 6 months, 1 year, and 2 years. In addition, patients will be contacted directly by email and text at least annually for up to 10 years to provide follow-up information via a dedicated portal maintained by the Icahn School of Medicine at Mt. Sinai.

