## 2.2 Rationale for Study Objectives Measures

## 2.2.1 To assess short-term and long-term safety

The safety of FMT is currently the greatest concern related to its use, and characterizing the safety of FMT and subsequent gut-related-microbiota products is the primary goal of the Registry. Short-term adverse events (AEs) relate primarily to the method of delivery (e.g., colonoscopy) and to acute infections or other adverse events from the donor fecal material and should be readily definable and quantifiable. Of greater concern and uncertainty is the possibility of long-term AEs. The human-to-human transfer of feces may be associated with long-term health risks to the recipient because the gut microbiota is composed of many components that have not been characterized and can change over time in ways that cannot be currently predicted. It is imperative to determine if FMT leads to unintended development of serious conditions due to the transfer of gut microbiota. In addition to infections, the possibility that gut microbiota associated with a disease phenotype (e.g., obesity, diabetes, cardiovascular disease) will be transplanted and result in chronic disease in recipients must be assessed. A prospective registry in a large sample of patients with long-term follow-up is the only practical method to achieve this aim at present.

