## 6.2 Classification of Events

#### 6.2.1 Relatedness

The site Investigator will assess the relationship of SAEs to FMT, as related or not related, based on clinical judgment and using all available information, and may include consideration of the following factors:

- Possible alternative causes of the SAE, including the disease under treatment, pre-existing
  conditions, concomitant use of other drugs, and presence of environmental or genetic
  factors.
- The temporal association between FMT exposure and onset of the SAE.
- Whether the manifestations of the SAE are consistent with known actions or theoretical toxicity of FMT.

The causal relationship between FMT and the SAE will be assessed using one of the following categories.

- 1. Not Related:
  - Temporal relationship is lacking (e.g., the event occurred before FMT); or
  - Other causative factors explain the event (e.g. pre-existing condition, other concomitant treatment);
- 2. Possibly Related:
  - Positive temporal relationship (e.g., the event occurred within a reasonable time frame following FMT); and
  - The SAE is possibly explained by FMT and/or, and there is a lack of other causal factors.
- 3. Related:
  - Positive temporal relationship (e.g., the event occurred within a reasonable time frame following FMT); and
  - The SAE is more likely explained by FMT than by other causes.

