## 8 Statistical Plan

## 8.1 Sample Size Determination and Power

As noted in the AHRQ's Registry User's Guide, registries are used to provide precise estimates of outcomes in real-world practice and document that potential adverse events occur at less than a pre-specified incidence with a predefined level of confidence. Plans for the FMT registry include a sample size of approximately 4,000 patients, which will provide precise estimates of incidence rates for common and rare events. For example, if the incidence of an outcome after FMT in the Registry population is 5.0%, the 95% CI will be 4.4% to 5.7%, indicating a precise estimate of treatment effect. The planned sample size will also provide high confidence in ruling out rare adverse events. If an adverse event does not occur in the planned population of 4000 patients, we will have 95% confidence that the adverse event occurs at a rate of less than one in a thousand patients undergoing FMT.

The FMT registry also will support comparative effectiveness studies focusing on different methods of delivery of FMT (e.g., colonoscopy, enema, upper GI endoscopy, nasogastric or nasointestinal tube). Statistical power for comparative effectiveness studies will depend upon the incidence of the outcome and the distribution of use of the different methods of delivering FMT. For example, assuming an outcome that occurs in one out of 1,000 FMT procedures using one delivery method, there would be 90% power to detect a difference between an incidence of 0.001 and 0.008 assuming that 2,000 patients were exposed to each of the two delivery methods. For more common outcomes, the statistical power for specific relative risk estimate is greater. For example, with 2,000 patients in each group there would be 90% power to detect a difference between two approaches for which the incidence rates of events were 3% and 5% (i.e., RR=1.67).

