## Supplement 5. FMT Short-term Adverse Outcomes (within 30 days)

- Procedure-related
  - Sedation complication
  - Bleeding
  - Perforation
  - o Other
- Symptoms post-FMT (within 30 days)
  - Diarrhea
  - Constipation
  - Nausea and/or vomiting
  - o Bloating
  - Abdominal pain
  - o Fever
  - Headache
  - Rash
  - Weight gain or loss
  - Other\_\_\_
- Surgeries or other Procedures
  - Describe
- Documented Infection (any)
  - Specify site/organism
  - o FMT related (related, possibly related, unrelated)
- Hospitalization
  - o Reason for hospitalization
  - o FMT related (related, possibly related, unrelated)
- Life-threatening experience
  - Describe/diagnosis
  - o FMT related (related, possibly related, unrelated)
- Death
  - Cause of death
  - o FMT related (related, possibly related, unrelated)
  - o Site of death
    - Hospital
    - Home
    - Convalescent or skilled nursing facility

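### Non-serious 30-day symptoms carry no severity or resolution item, so symptom rates and delivery-method comparisons cannot separate brief mild symptoms from severe or persistent ones

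*Protocol*

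**What the plan says.** Safety is the primary objective (protocol section 2.1). Section 6.1 names the instruments: "to broadly capture adverse outcomes in recipients of FMT that may be indicative of a safety concern, we have developed two data entry fields", namely Supplement 5 (first 30 days) and Supplement 6 (later, by physician to 2 years and by patient to 10 years).

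- **Supplement 5.** Under "Symptoms post-FMT (within 30 days") it names diarrhea, constipation, nausea or vomiting, bloating, abdominal pain, fever, headache, rash and weight change. None has a severity, duration or resolution item. On the same form, infection, hospitalization, life-threatening experience and death each carry "FMT related (related, possibly related, unrelated"), together with a site and organism, reason, description or cause.
- **Supplement 6.** It covers new diagnoses, new drugs, procedures, serious infection, hospitalization, life-threatening illness and death. Apart from recording weight, it has no item for a 30-day symptom that continues.
- **Classification.** Section 6.2.1 states "The site Investigator will assess the relationship of SAEs to FMT", and 6.2.2 judges expectedness of related or possibly related SAEs. Neither grades a non-serious event, and the protocol gives no AE severity scale.
- **Intended use.** Section 2.2.1 says "Short-term adverse events (AEs) relate primarily to the method of delivery (e.g., colonoscopy"). Section 8.1 plans comparisons of delivery methods, for example that "with 2,000 patients in each group there would be 90% power to detect a difference between two approaches" with event rates of 3% and 5%.
- **Status and follow-up.** Section 5.1 introduces the lists with "Data elements that may be collected for the FMT registry are shown in Supplements 1-6" and adds "Patients will be followed at regular intervals for up to 10 years after FMT for pre-defined and spontaneously reported adverse events".

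**The concern.** Two patients who tick abdominal pain give the same entry, even if one had a mild ache for a day and the other had severe pain for weeks that was managed without admission. If the second patient's pain is still there at 6 months, no predefined question asks about it. It reaches the registry only if someone volunteers it, or if it leads to a new diagnosis, drug, procedure or admission.

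This matters because the protocol expects short-term harm to follow the delivery method and intends to compare methods. An excess of mild, self-limiting symptoms with one method and an excess of severe or lasting symptoms with it would look alike. The second kind of excess may also go undetected against a common mild background. An analysis plan can choose which rates to report, but it cannot recover an attribute that was not collected.

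**Working it through.** **1. What is and is not recorded**

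| Event | Predefined detail | Followed by a predefined later item? |
|---|---|---|
| Death, life-threatening event, hospitalization | Cause, description or reason; relatedness | Yes, Supplement 6 |
| Infection | Site and organism; relatedness | Serious infection only, Supplement 6 |
| Other SAE, including disability or permanent damage (6.3) | Relatedness (6.2.1); expectedness if related or possibly related (6.2.2) | Through SAE recording |
| Diarrhea after FMT for CDI | Tick in Supplement 5; cure, recurrence and timing in Supplement 4 | Partly, as an effectiveness outcome |
| Weight change | Tick in Supplement 5 | Weight in Supplement 6 |
| Other non-serious symptoms | Tick only | No |

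The gap is confined to non-serious symptoms. Supplement 4 already grades IBD after FMT from quiescent to severe, so grading on these forms is feasible.

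**2. Reproducing the plan's own power figures**

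Inputs from section 8.1: n = 2,000 per group; rates 3% versus 5% and 0.001 versus 0.008; stated power 90%. Alpha is not stated; I assume two-sided 0.05, in line with the 95% intervals.

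With d the difference between the rates and p̄ their mean:

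- s0 = √[2p̄(1−p̄)/n]
- s1 = √{[p1(1−p1) + p2(1−p2)]/n}
- power = Φ[(d − 1.96·s0)/s1]

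For 3% versus 5%: p̄ = 0.04, s0 = 0.00620, s1 = 0.00619, so Φ[(0.02 − 0.01215)/0.00619] = Φ(1.27) = 89.8%. For 0.001 versus 0.008 the same formula gives 91.1%. Both agree with the stated 90%.

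**3. A severe excess recorded separately, or inside an ungraded item**

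Assumed: severe symptoms in 2% versus 4%, with the two-point excess carried in full into a yes/no item whose rate in the lower group is 20% to 50%. The documents give no symptom rates, so the range is illustrative.

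| Comparison | s0 | (d − 1.96·s0)/s1 | Power |
|---|---|---|---|
| 2% vs 4%, severe recorded separately | 0.00539 | 1.75 | 96% |
| 20% vs 22%, ungraded | 0.01288 | −0.41 | 34% |
| 30% vs 32%, ungraded | 0.01463 | −0.59 | 28% |
| 40% vs 42%, ungraded | 0.01555 | −0.67 | 25% |
| 50% vs 52%, ungraded | 0.01581 | −0.69 | 24% |

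The relative risk shrinks from 4/2 = 2.0 to between 22/20 = 1.10 and 52/50 = 1.04.

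**4. The same check on the plan's own 3% and 5%**

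Take these as severe-symptom rates and add an assumed mild rate m, equal in both groups and independent of severe symptoms. The item's rate is then 1 − (1 − s)(1 − m). With m = 10% this gives 1 − 0.97 × 0.90 = 12.7% and 1 − 0.95 × 0.90 = 14.5%.

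| m | Item rates | Power |
|---|---|---|
| 0 | 3.0% vs 5.0% | 89.8% |
| 5% | 7.85% vs 9.75% | 56.4% |
| 10% | 12.7% vs 14.5% | 38.2% |
| 30% | 32.1% vs 33.5% | 15.5% |

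The loss is already material at a 5% mild background. If the 3% and 5% are instead SAEs or hospitalizations, analysed in their own fields, power stays at 89.8%.

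**The case against.** The strongest reply has four parts.

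- **Serious harm is protected.** It has its own criteria in 6.3, including disability, and its own fields in both supplements. This stands. A reader might infer that mild symptoms swamp severe harm throughout the safety rates, but the documents do not support that: section 8.3 defines no pooled any-symptom endpoint, and Supplement 5 lists each symptom separately. The loss arises within a symptom item that mixes mild and severe cases, or if an analyst pools the items.
- **Follow-up does not stop at day 30.** A reader might infer from the 30-day heading that it does. Sections 5.1, 6.1 and 6.4 contradict this: sites report at 1, 6, 12 and 24 months, patients at least annually to 10 years, and all spontaneous events are recorded. What is missing is a structured prompt for a persisting symptom. Section 8.3 itself faults systems that rely on spontaneous reporting for incomplete numerators, so that route is a weak substitute.
- **The supplements list what may be collected; they are not the eCRF.** This is a fair caution, since the eCRF could hold more. Yet section 5.1 describes the lists as deliberately broad, the protocol promises no severity field, and the same form adds detail to other events.
- **A short checklist is defensible in a 75-site registry whose greater worry is long-term harm.** This argues for a small change. It also tells against grading every AE out to 10 years, because the site does not see patient-portal reports first-hand.

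**Conclusion.** The point holds for non-serious symptoms only. As specified, their 30-day incidences, and any delivery-method comparison based on them, cannot distinguish brief mild symptoms from severe or persistent ones that do not meet an SAE criterion. Rates of SAEs, hospitalization, life-threatening events and death are not affected, and the power statements in 8.1 are arithmetically sound.

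The illustrated size is a fall from 96% to between 24% and 34% for a 2% versus 4% severe-symptom difference. It rests on assumed symptom rates, an assumed two-sided 0.05, the protocol's 2,000 per group, and the severe excess being neither offset nor graded within the item. It also assumes that the eCRF holds no more than Supplement 5 lists. This is an inexpensive improvement to the instrument for the primary objective; it does not invalidate the registry's safety estimates.

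**What to change.** 1. **Supplement 5:** for each ticked symptom add severity (mild, moderate, severe) and whether it is still present at the 1-month report (yes/no). If the eCRF already holds these fields, state so in the protocol.
2. **Supplement 6:** carry any symptom marked as still present to the site's existing 6-month form.
3. **Section 8.3:** report the incidence of moderate-or-worse and of persistent symptoms beside the incidence of any symptom, including in delivery-method comparisons. Keep the any-symptom rate.

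No grading of all AEs to 10 years is needed. This changes data capture only and requires no extra visit, procedure or staff. The costs are slightly more form time and reliance on site judgement for severity. Patients already past the 1-month form cannot be reliably graded, so the graded rates would apply from the date of the change and should be reported with their own denominator.
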